8.7 Risk-to-benefit rationale

The risks from all identified hazardous situations have been considered [15]. It is concluded that the clinical benefit of using the device is greater than the residual risks, and the overall residual risk associated with the product are judged to be acceptable [16]. Using the device adds no extra risk to the risk found for the absorbing incontinence products. The device is intended to be used in combination with these products. Absorbing incontinence products have been on the market for many years and showed to be low risk devices with a clear clinical benefit.

The risk management activities are in line with the risk management plan [17], the risk management procedure [18] and the requirements of the EN ISO 14971:2019 standard. The risk management have been made with regard to the general safety and performance requirements of the Medical Device Regulation 2017/745.

	Title: POWER Clinical Investigation Plan	Id:
---	---	-----

9 OBJECTIVES AND HYPOTHESES OF THE CLINICAL INVESTIGATION

9.1 Primary Objective

The primary objective of this clinical investigation is to demonstrate performance through the ability to reduce the number of manual checks in-between the daily changes of absorbing incontinence products using the TENA SmartCare Change Indicator compared to Standard of Care.

9.2 Secondary Objectives

The secondary objectives are to:

- Evaluate safety through analyzing device-related adverse events reported during the investigation.
- Evaluate leakage into clothes and/or bed linen.
- Evaluate change in skin redness and irritation.
- Evaluate usability.
- Evaluate the number of fecal incidences.

9.3 Hypothesis

The null hypothesis (H_0) is that there is no difference in the mean number of checks performed during the investigation week compared to the baseline week.

The alternate hypothesis (H_1) is that there is a reduction in the mean number of checks performed during the investigation week compared to the baseline week.

9.4 Claims and intended performance of the investigational device

The device has no specific claim for performance other than what is stated in its intended use and indication.

- The TENA SmartCare Change Indicator estimates the degree of urine saturation in the absorbing incontinence product and notifies the care giver. It is to be use on individual(s) suffering from urinary incontinence in a home or professional environment who are dependent on one or more caregivers to change the individual's absorbing incontinence products.

The device has no specific claim for safety other than that it is safe to use when used as intended.

9.5 Risks and anticipated device effects

There are no anticipated device effects, the device is used in combination with an absorbing incontinence product which have the primary function to alleviate the incontinence issues suffered by the DEU. There are no unacceptable risks connected to participating in the investigation besides the residual risks reported in section 8.3.

	Title: POWER Clinical Investigation Plan	Id:
---	---	-----

10 DESIGN OF THE CLINICAL INVESTIGATION

10.1 General

This is a prospective, interventional, post-market clinical investigation with the aim to demonstrate the performance and safety of the TENA SmartCare Change Indicator when used as intended in subjects affected with UI compared to Standard of Care. The outcome will be evaluated and incorporated in the product specific CER and serve as a base for continuous investigations.

Thirty-five (35) DEUs with UI cared for in a home environment mainly by one CGR will be recruited in Poland.

The clinical investigation is designed to be conducted in the individuals home environment, for a duration of three (3) weeks + potential incontinence product training week (one) and potential additional days depending on the visit window scheduling. Eight visits are planned for each subject during the duration of the clinical investigation. However, two of the visits are optional and conducted as needed. If considered necessary by the investigator, nurse, or CGR, additional contacts (e.g. visits/phone calls/video calls) can be arranged. The first week will establish an individual baseline for each EDU, during which the number of manual daily checks between changes of the TENA incontinence product are to be registered by the CGR. During the second week the CGR will be provided the TENA SmartCare Change Indicator and learn how to set up and use it as intended by the manufacturer. During the third week the TENA SmartCare Change Indicator will be used as intended by the manufacturer, while the number of additional manual checks between changes of the TENA incontinence product are to be registered by the CGR. The number of manual checks will be analyzed with regard to the individual baseline in order to evaluate the reduction of manual checks.

The overall duration of the investigation is estimated to 8 months, including a 6-month recruitment period. Expected duration of each subject's participation is 3-6 weeks depending on potential incontinence product training week and potential additional days depending on the visit window scheduling.

10.1.1 Primary Endpoint

- Change in the number of manual checks in-between the daily changes of the absorbing incontinence product at week 3 (investigational week) compared to week 1 (baseline week).

10.1.2 Secondary Endpoints

- Incidence of adverse events during week 2 (learning week) and week 3 (investigational week); adverse events (AE), adverse device effects (ADE), serious adverse events (SAE), and serious adverse device effects (SADE), and device deficiency (DD).
- Change in the number of leakages into the clothes and/or bed linen at week 3 (investigational week) compared to week 1 (baseline week).
- Evaluate change in skin redness and irritation, at week 3 (investigational week) compared to week 1 (baseline week).
- Evaluate usability (questionnaire week 2 and 3).
- Evaluate the number of fecal incidences.

	Title: POWER Clinical Investigation Plan	Id:
---	---	-----

10.2 Investigational device(s) and comparator(s)

This is a single arm clinical investigation. The DEU will act as its own control and documented checks during the investigational week will be compared to the Standard of Care during the baseline week.

Each participating CGR will be provided with the investigational product; TENA SmartCare Change Indicator (sensor and app), as well as single use TENA incontinence products. The single use TENA incontinence products will be used during the entire study period. CGR will receive enough products throughout the clinical investigation. TENA SmartCare Change Indicator is a re-usable medical device accessory to be used with single use TENA incontinence products. TENA SmartCare Change Indicator will be provided to each participating CGR/EDU, with the assumption that one product per subject will be needed. In case of malfunction, the investigational product will be replaced. To ensure this is made in a timely manner the CGR will be provided with an extra set of transmitter and sensor strips. These will be accounted for and traced similar to all other study devices.

Within the scope of this clinical investigation, no other additional medical device or medication is required.

10.3 Subjects

10.3.1 Inclusion Criteria

The DEUs and/or CGRs must meet all of the following criteria to be eligible for this clinical investigation:

1. DEU is diagnosed with urinary incontinence managed with a tape-style incontinence product.
2. DEU is unable to sufficiently communicate the need for an incontinence product to be changed.
3. DEU is being cared for in a home environment and most of the care is provided by a main CGR.
4. DEU is willing and able to provide informed consent and to participate in the clinical investigation or has a legally designated representative willing to provide informed consent on behalf of the DEU. Note, the legally designated representative and main CGR cannot be the same person.
5. CGR is willing and able to provide informed consent to participate in the clinical investigation.
6. The CGR frequently checks the saturation level of the incontinence product, manually and/or by a touch-feel process.
7. If incontinence is managed by pharmaceuticals, the dose regime is stable.
8. DEU and CGR ≥ 18 years of age.

10.3.2 Exclusion Criteria

DEUs and/or CGRs meeting any of the following criteria will not be permitted to participate in the clinical investigation:

1. DEU is cared for in a professional establishment or is institutionalized.
2. DEU has ≥ 4 fecal "incidences" per week.
3. DEU has severe incontinence product related skin problems, as judged by the investigator.
4. DEU has any type of urinary catheter(s) resulting in improved/treated urinary incontinence.
5. The incontinence product is changed on a routine based on time (schedule) or device alert, without manual checks.

	Title: POWER Clinical Investigation Plan	Id:
---	---	-----

6. Any other condition that may make participation in the clinical investigation inappropriate, as judged by investigator.
7. CGR is incapable or unwilling to use the required smartphone application and/or the diary registration webpage required for the clinical investigation.
8. Participation in an investigational study of a drug, biologic, or device within 30 days prior to entering the clinical investigation or planned during the course of the clinical investigation.
9. DEU is pregnant or nursing.
10. CGR or DEU with an alcohol or drug addiction

10.3.3 Relationship of investigation population to target population

The TENA SmartCare Change Indicator is intended to be used in adults diagnosed with urinary incontinence, who are unable to sufficiently communicate the need to change an incontinence product to a caregiver. For this investigation the caregiver is a care giving relative (CGR) that will use the device in a home environment.

10.3.4 Number of Subjects

The investigation population will be comprised of 35 DEUs suffering from UI, cared for in a home environment mainly by one CGR, and that are fulfilling all of the inclusion criteria and none of the exclusion criteria for the clinical investigation. For details linked to sample size calculations, see section 12.2.

10.3.5 Methods of Assigning Subjects to the different treatment arms

Not applicable as this is a non-randomized single arm clinical investigation.

10.3.6 Subject withdrawal or discontinuation

DEUs and/or CGRs are free to discontinue participation in the clinical investigation at any time and are not required to give a reason for their decision. However, DEUs and/or CGRs who discontinue the investigation should always be asked about the reason(s) for their discontinuation and about the presence of any AE/ADE and, if possible, be assessed by an investigator. Discontinuation from the clinical investigation will not affect the future treatment/care of the DEU or the CGR. In case a CGR withdraws from the study, the respective DEU can not participate in the study anymore.

If the DEU/CGR withdraws his/her consent no further data will thereafter be recorded. Data collected up to the date of withdrawal of informed consent will be used in the data analysis and for the Clinical investigation Report (CIR), provided that the subject and or CGR do not actively request all data to be removed.

Participants may be withdrawn from the clinical investigation and assessments at any time, if deemed necessary by the investigator.

Specific reasons for withdrawal of participants from this clinical investigation are:

- The decision of a DEU/CGR to withdraw from the investigation.
- The investigator deems the DEU/CGR unfit for the investigation or suspects poor CIP compliance.
- DEU/CGR lost to follow-up.

In case of withdrawal, all AEs/ADEs should be followed up until the event is resolved or judged as stable by the sponsor, if possible. Applicable documentation should be returned to the Sponsor.

	Title: POWER Clinical Investigation Plan	Id:
---	---	-----

Incorrectly enrolled subjects will be withdrawn from further investigation and assessments. A subject may, however, continue the clinical investigation under exceptional circumstances (i.e. if continuation of investigation or follow-up are necessary for the subject's safety and wellbeing, or if only a follow-up period remain, and the continuation of the investigation is not expected to be associated with any risk or discomfort for the subject).

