13.1 Data Retention

The medical files of clinical investigation subjects must be retained in accordance with local legislation and in accordance with the maximum period of time permitted by the hospital, institution or private practice.

The investigator shall retain all clinical investigation records during the investigation and for the period required by the applicable regulatory requirements or for at least 10 years after the premature termination or completion of the clinical investigation, whichever is the longer. The PI must take measures to prevent accidental or premature destruction of these documents. The PI should contact the sponsor prior to destruction of any records or reports pertaining to the clinical investigation in order to ensure they no longer need to be retained. In addition, if the PI leaves the hospital, he/she should provide the sponsor with the name and address of the person who will look after and be responsible for the clinical investigation-related records. If the records will be transferred to another person/party, the transfer will be documented at the investigation site and/or at the Sponsor.

	Title: POWER Clinical Investigation Plan	Id:
---	---	-----

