19.4 Reporting of SAE/SADE and Device Deficiencies with SADE potential

All SAEs, whether or not related to the investigational medical device or procedure involved shall be entered into the eCRF.

The following events are considered reportable events according to MDR 2017/745:

- a) Any SAE that has a causal relationship with the investigational device, the comparator or the investigation procedure or where such causal relationship is reasonably possible;
- b) Any Device Deficiency that might have led to a SAE if:
 - a. appropriate action had not been taken, or
 - b. intervention had not occurred, or
 - c. circumstances had been less fortunate.
- c) Any new findings in relation to any event referred to in points a) and b).

The above must be reported to the Sponsor immediately, without unneccary delay, after investigational site investigation personnel's awareness of the event, regardless of the time that may have elapsed from the time the event occurred.

The initial report should contain as much information as possible, but as a minimum the following information:

- Subject identification.
- Site contact information.
- Date of procedure/first use.
- Date of event onset.
- Event type (i.e. SAE or DD with SADE potential).
- Description of event.
- Action/treatment/subject outcome.
- Relationship to investigation procedure.
- Relationship to medical device.
- Unanticipated SADE (Yes/No).
- Treatment Arm.
- Event status.

The Sponsor must also promptly receive a completed report. All SAEs have to be reported whether or not they are considered causally related to the investigational medical device.

	Title: POWER Clinical Investigation Plan	Id:
---	---	-----

SAE/SADE EMERGENCY CONTACT DETAILS

Name: [name]

Address: Essity Hygiene and Health AB, [name]

Phone:

E-mail:

Since this is a post-market clinical investigation all reportable events will be handled according to the Sponsors vigilance system and in accordance with MDR 2017/745.

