#### **4.2.1 Safety Analysis Set (SAF)**

The SAF will consist of all consented subjects.

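### Protocol 10.3.6 drops a withdrawn pair's earlier data from the analysis on request, with no exception for safety records and no rule for counting such pairs in the safety set

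*Protocol*

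**What the plan says.** Protocol 10.3.6 sets the rule. Once consent is withdrawn, recording stops: "If the DEU/CGR withdraws his/her consent no further data will thereafter be recorded". What was collected earlier goes into the analysis and the clinical investigation report, on the condition "provided that the subject and or CGR do not actively request all data to be removed". The condition covers data of every kind and does not set safety records apart.

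The same section says that people who discontinue "should always be asked about the reason(s) for their discontinuation and about the presence of any AE/ADE". It also says "In case of withdrawal, all AEs/ADEs should be followed up until the event is resolved or judged as stable by the sponsor", if possible.

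Elsewhere in the plan:
- Protocol 10.1.2 makes the incidence of AEs, ADEs, SAEs, SADEs and device deficiencies in weeks 2 and 3 a secondary endpoint.
- SAP 4.2.1: "The SAF will consist of all consented subjects".
- SAP 4.7 uses what is available from withdrawn subjects where it can, and imputes nothing. It does not mention removal requests.
- SAP 8 declares no changes from the protocol. SAP 9 plans a listing of discontinued patients but none of removal requests.
- Protocol 13.1: "The investigator shall retain all clinical investigation records during the investigation and for the period required by the applicable regulatory requirements", or at least 10 years if that is longer.
- Protocol 19.4: "All SAEs, whether or not related to the investigational medical device or procedure involved shall be entered into the eCRF".

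**The concern.** Following the clause as written can take recorded events out of a safety endpoint after they have been observed. Removal depends on the participant's choice, and that choice may be related to what happened with the device. If pairs with a bad experience ask for removal more often than others, the reported incidence is too low.

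The safety assessment has no comparator group and about 35 subjects, so one or two records visibly move a percentage. SAP 7.3.3 also plans a count of subjects who stopped the device because of an AE. These subjects have already left the device, so this row is the most exposed. Because no table or listing of removal requests is planned, a reader of the report could not tell whether any had occurred.

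**Working it through.** **1. Does another passage override the clause?** The candidates, set beside it:
- SAP 4.2.1 puts every consented subject in the safety set. A pair that later asks for removal did consent, so read literally it stays in the denominator. But its event records may no longer be used, and no rule says whether it counts as a subject without events, as missing, or not at all.
- SAP 4.7 speaks of available data. Removed data are not available.
- Protocol 13.1 requires records to be retained. The clause in 10.3.6 governs use in the analysis and the report, so records can be kept and still left out of the tables. This is not a contradiction, and it does not protect the tables either.
- Protocol 19.4 requires SAEs to be entered in the eCRF when they occur. A later request does not contradict that, and 19.4 does not say that the entry stays in the analysis.

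None of them overrides the clause.

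**2. Inputs for the size.** 24 evaluable subjects and 30% drop-out (Protocol 12.2). The plan's figure reproduces: 24 / (1 − 0.30) = 34.3, rounded up to 35. That leaves 35 − 24 = 11 pairs who may drop out for any reason. Numbers of events and of removal requests are not given, so those below are assumptions.

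**3. Effect on a reported incidence.** With e subjects having an event among 35, of whom r have their data removed, the reported proportion is (e − r) / (35 − r) if the pair leaves both numerator and denominator.

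| e | r | All data kept | Reported after removal |
|---|---|---|---|
| any | 0 | e/35 | unchanged |
| 2 | 1 | 2/35 = 5.7% | 1/34 = 2.9% |
| 4 | 2 | 4/35 = 11.4% | 2/33 = 6.1% |
| 4 | 3 | 4/35 = 11.4% | 1/32 = 3.1% |
| 4 | 4 | 4/35 = 11.4% | 0/31 = 0% |

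For the third row the exact (Clopper-Pearson) 95% intervals are 3.2 to 26.7% with all data kept and 0.7 to 20.2% after removal.

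**4. Effect of the missing counting rule.** If the two removed pairs stay in the denominator because they consented, the third row becomes 2/35 = 5.7% (0.7 to 19.2%). Either convention roughly halves the 11.4%. Keeping the subjects without their records does not solve the problem.

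**5. Two sentences of 10.3.6 side by side.** One says that nothing more is recorded after consent is withdrawn. The other says that AEs and ADEs are followed up in case of withdrawal. The section does not say whether the second applies only to people who stop participating without withdrawing consent, or how a follow-up outcome could be documented once recording has ended.

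**The case against.** The case against giving this much weight is substantial, and most of it stands.

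- **Retention is the default.** Removal needs withdrawal of consent and then an active request for removal of all data. The 30% drop-out covers every cause, including loss to follow-up and withdrawal by the investigator, and neither of those triggers the clause. A reader might infer that several of the 11 expected drop-outs would ask for removal; nothing in the documents supports a number.
- **Harm as the reason for leaving.** A reader might infer that the pairs who leave are those who were harmed. Protocol 8.2 anticipates no adverse device effects and reports none in the previous investigation, and drop-out is not broken down by reason. Selective removal is plausible but is an inference.
- **Complete loss of serious events.** A reader might picture a SADE disappearing, so that 1/35 (2.9%) is reported as 0/34. Serious events have the most parallel records. SAEs are reported to the sponsor, and reportable events go through its vigilance system (Protocol 19.4). Device deficiencies go to the sponsor on their own form (19.3). AEs, ADEs and device deficiencies are also noted in the medical records (11.1). Such an event could be missing from a table, but the sponsor would know of it.
- **The caregiver acting alone.** The wording can mean that either party may remove everything, or that each may remove their own data. Caregivers consent separately and have their own data collected. The text is loose and does not settle which is meant.
- **Limited consequence.** Safety is summarised descriptively without tests (SAP 7.3.2), and the pass/fail criterion (Protocol 12.5) concerns manual checks only. A pair that leaves before week 3 has no week 1 to week 3 change to lose, so the effect on the primary analysis is thin.
- **Participants' rights.** Abolishing removal for all data would be a real trade-off in a population that includes adults unable to consent, and Protocol 18 invokes national data legislation and GDPR. The consent forms and the data management plan may say more, but they are not part of the documents at hand.

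These points narrow the concern to non-serious events in the report's tables. They do not remove it: the clause is a stated rule without a safety exception, and no passage in the protocol or SAP limits it.

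**Conclusion.** The concern holds in this narrow form. Protocol 10.3.6 permits recorded safety data to be left out of the analysis and report on request, and the SAP does not say how the affected pairs are counted. The realistic exposure is that non-serious AEs and ADEs, and possibly the subjects who had them, drop out of the descriptive safety tables.

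The size depends entirely on assumed counts. With 4 events and 2 removals, 11.4% is reported as 6.1%, or as 5.7% if the pairs stay in the denominator. With no requests there is no effect. No sample-size figure changes, and the primary conclusion is essentially untouched. The retention and SAE-entry requirements do not contradict the clause. The two points to settle are its interaction with SAP 4.2.1 and the pair of sentences within 10.3.6. This is a cheap improvement worth making, not a flaw that undermines the trial.

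**What to change.** Amend Protocol 10.3.6, SAP 4.2.1 and 4.7, and the consent forms as follows.

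1. Subject to the data-protection law that the protocol invokes, AE, ADE, SAE, SADE and device deficiency records made before withdrawal stay in the safety set in coded form, with the consent and exposure record.
2. A caregiver's request covers the caregiver's own data and does not by itself remove the DEU's safety records.
3. The report gives the number and timing of removal requests, and the SAP states how the pairs concerned are counted.
4. The two sentences in 10.3.6, on ending recording and on following up AEs and ADEs after withdrawal, are reconciled so that sites know which situations each covers.

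The participant's option to remove other data can remain. The cost is a short amendment to the protocol, SAP and consent forms, with notification of the ethics committee. The downside is small: participants have less control over coded safety data already collected.

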12.2 Sample size

The sample size calculation is based on the assumption of a reduction of the number of manual checks in-between incontinence product changes by 30%. Based on data from [20] and the statistical power in section 12.3 this give a sample size of 24 subjects. Assuming a 30% dropout rate, the investigation will include up to 35 subjects. If for any reason the dropout rate should be higher than this, additional subjects might be enrolled in the investigation to reach a total of 24 completed subjects.

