#### **4.2.2 Full Analysis Set (FAS)**

The FAS will include all subjects included in the SAF and have at least one set of efficacy measurements after using the investigational device.

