#### **4.2.4 Use of Analysis Sets**

The presentation of safety data will be based on the SAF.

The presentation of baseline characteristics and demographics will be based on the FAS.

	Title: Statistical Analysis Plan	Id: Version 2.0_25-Nov-2021
---	-------------------------------------	--------------------------------

The primary endpoint analysis will be performed using both the FAS and the PPS. The FAS will be considered as the main analysis.

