### 6.4 Compliance of Study Device

Compliance of the study device will be determined by observing that the devices are being used as is registered in the device system.

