### 7.1 Primary efficacy endpoint

#### 7.1.1 Definition

The primary efficacy endpoint is the change in percentage of the number of manual checks between week 1 and week 3 of the investigation. The average manual checks/day for a subject week will be used for the percentage calculation, since data may be available for less or more than 7 days.

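### CIP 10.3.6 allows withdrawal from assessments on undefined, suspected poor compliance, so pairs who make little use of the device can be left without a week-3 value

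*Protocol*

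**What the plan says.** **Withdrawal.** CIP 10.3.6 gives a general power: "Participants may be withdrawn from the clinical investigation and assessments at any time, if deemed necessary by the investigator". Among the specific reasons it then lists is "The investigator deems the DEU/CGR unfit for the investigation or suspects poor CIP compliance". Neither sentence has a definition or threshold. The two members of a pair are tied together: "In case a CGR withdraws from the study, the respective DEU can not participate in the study anymore".

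**Primary variable.** SAP 7.1.1 uses the percentage change in checks from week 1 to week 3: "The average manual checks/day for a subject week will be used for the percentage calculation, since data may be available for less or more than" seven days.

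**Analysis sets and missing data.** FAS subjects must be in the safety set and "have at least one set of efficacy measurements after using the investigational device". SAP 4.2.4 adds: "The FAS will be considered as the main analysis". The PPS is a subset of the FAS. Under SAP 4.7, whatever data withdrawn subjects have provided are used, and missing values are not imputed. CIP 12.11 plans no exclusions from the hypothesis test.

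**Numbers.** CIP 12.2 and SAP 4.1 need 24 subjects and assume 30% drop-out, giving up to 35. If drop-out exceeds that, "additional subjects might be enrolled in the investigation to reach a total of 24 completed subjects".

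**Visibility of device use.** SAP 6.4 states: "Compliance of the study device will be determined by observing that the devices are being used as is registered in the device system". Correct use is also checked at the optional Visits 4 and 6, and the learning-week diary is confirmed at Visit 5, before week 3 begins.

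**The concern.** The objective is to show that the device reduces manual checks compared with Standard of Care in home use. A caregiver who is given the device and makes little use of it is part of the answer to that question, and probably an unfavourable part.

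The withdrawal rule ends assessments as well as participation. It can be applied on suspicion, after staff have had a chance to see how the pair is using the device. If it is applied before week 3, the primary value is never collected, and no later analysis can recover it. Because the FAS result and the PPS result lose the same pairs, comparing them would not show the selection. The planning assumption is a 30% reduction and the pass criterion in CIP 12.5 is more than 30%, so a moderate selection effect could matter.

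**Working it through.** **1. What happens to a withdrawn pair**

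| Time of withdrawal | Week-3 diary data | Primary value |
|---|---|---|
| Learning week, or at Visit 5 | None | None. The pair may formally meet the FAS definition through its learning-week diary, but has no week-3 average |
| During week 3 | Some days | Yes, from the available days, because the endpoint is a daily average |

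The gap therefore concerns pairs withdrawn before week 3. Using available data, not imputing, and planning no exclusions cannot supply a count that was never recorded. The sentence in 10.3.6 that recording stops concerns withdrawal of consent. For withdrawal by the investigator, the diary ends because assessments end.

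**2. The plan's own figure**

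24 / (1 − 0.30) = 34.3, rounded up to 35, which reproduces the plan. The allowance is 35 − 24 = 11 pairs (11/35 = 31%) that can leave with 24 completers remaining.

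**3. Effect on the mean (assumed values)**

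Let all 35 pairs receive the device, k of them make no real use of it and show 0% change, and the others average a reduction of R%. Keeping everyone gives R × (35 − k)/35. Removing the k pairs gives R. The upward shift is R × k/35.

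| R | k | All 35 kept | k removed | Shift (points) |
|---|---|---|---|---|
| 40% | 4 | 40 × 31/35 = 35.4% | 40% | 4.6 |
| 40% | 8 | 40 × 27/35 = 30.9% | 40% | 9.1 |
| 40% | 11 | 40 × 24/35 = 27.4% | 40% | 12.6 |
| 30% | 11 | 30 × 24/35 = 20.6% | 30% | 9.4 |

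With R = 40%, the all-pairs mean falls below 30% only from k = 9 (40 × 26/35 = 29.7%).

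**4. Effect on the 30% criterion (assumed values)**

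SAP 7.1.2 checks the 30% reduction with a one-sided 95% confidence interval, so the SD matters, and none is given. If 24 came from a one-sided paired t-test of a 30-point reduction at alpha 0.05 and 90% power, the implied SD is about 49 points (normal approximation: 30 × √24 / (1.645 + 1.282) ≈ 50). The simulation used 20,000 normal samples, 35 pairs and the same SD for users and non-users. It gives the chance that the lower bound exceeds 30%:

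| R | k | SD | All kept | k removed |
|---|---|---|---|---|
| 50% | 7 | 48 | 28% | 69% |
| 50% | 7 | 25 | 58% | 99% |
| 40% | 11 | 48 | 2% | 26% |
| 40% | 11 | 25 | 0.4% | 60% |

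In the rows with R = 50%, the all-pairs mean is 50 × 28/35 = 40%, so removal overstates a real effect. In the rows with R = 40% the all-pairs mean is 27.4%, below the criterion, but this needs every pair in the allowance to be a non-user. The test against no change is hardly touched: with R = 40%, k = 11 and SD 48, the chance that the lower bound exceeds zero is 94% if all are kept and 99% if the k pairs are removed.

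**The case against.** **Checking by hand is not a breach.** A reader might infer that the rule targets caregivers who keep checking. The documents do not support that. CIP 10.1 expects additional manual checks in week 3, and CIP 6 presents the device as a complement to manual checking. Nor does any section equate low device use with poor compliance. The planned response to difficulties is support at Visits 4 and 6. This stands. What remains is that the undefined wording permits such a reading, since CIP 10.1 also has the device used as intended in week 3.

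**Visibility is partly inferred.** SAP 6.4 does not say who sees the device-system data or when, Visits 4 and 6 are optional, and nurses run Visits 2 to 6 while the investigator decides on withdrawal. This weakens the likelihood of selection but does not close the route.

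**Withdrawn pairs are not freely replaced.** A reader might infer replacement one for one. CIP 12.2 allows extra enrolment only when drop-out exceeds 30%.

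**Small examples can mislead.** With 24 completers at 33% and three removed pairs at 0%, the combined mean is 33 × 24/27 = 29.3%, which looks like a lost pass. But 27 assumes eight unrelated losses out of 35. With 32 completers it is 33 × 32/35 = 30.2%. It also compares point estimates. With n = 24 and a mean of 33%, the lower bound 33 − 1.714 × SD/√24 exceeds 30% only if the SD is below about 8.6, and at SD 49 it is about 16%. The example shows direction, not a changed conclusion.

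**Use as intended is a legitimate question.** CIP 10.1 aims at performance when the device is used as intended. That analysis belongs in the PPS, where major deviations are already handled. It does not justify leaving the data for the FAS uncollected.

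**Removals would be visible.** Reasons for discontinuing are asked for, and discontinued patients are listed. That shows how many left, but not what their week-3 counts would have been.

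**Conclusion.** The concern holds as a gap in the wording. CIP 10.3.6 permits assessments to end on undefined, suspected poor compliance, and nothing provides for the diary to continue. Pairs withdrawn this way before week 3 have no primary value in either analysis set, which could bias the estimated reduction upward.

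The size cannot be determined from the documents. Under the assumptions shown (non-users at 0%, a 40% reduction in users), the shift runs from 4.6 points with 4 such pairs to 12.6 points with 11. If non-users also reduced their checks, or if few were withdrawn, the shift would be smaller. The documents do not show that such withdrawals are intended or likely, that they would be replaced below 30% drop-out, or that the 30% criterion would be crossed because of them. Pairs withdrawn during week 3 are not lost. The change is still worth making before data are collected, because it is cheap and the missing counts cannot be recovered later.

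**What to change.** **CIP 10.3.6.** State that suspected poor compliance, including low or stopped device use, is recorded as a CIP deviation and is not by itself a ground for ending assessments. Apply this also to the general sentence on withdrawal at the investigator's discretion; otherwise the same route stays open. Leave withdrawal for unfitness, safety or participant choice unchanged. State that pairs who still consent complete the week-3 diary and Visit 7.

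**SAP 4.2.2.** Define the FAS as subjects given the device at Visit 3 who have any week-3 diary data. The present wording depends on having used the device, so a pair given it but never using it would fall outside.

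**SAP 4.2.3 and 5.1.** Handle device-use deviations in the PPS only, and report withdrawals by reason and by week.

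**SAP 7.1.2.** Add a sensitivity analysis that sets the change to 0% for pairs given the device who have no week-3 data.

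**Cost.** A short CIP and SAP amendment. No visits are added, since the diary and Visit 7 are already planned. The FAS reduction may be somewhat smaller.
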